6.0 Data Management Plan

6.1 Data Analysis

The site PI and treatment team will meet on a daily basis to review the data and the safety of participants. The investigators will graph and analyze the data for all participants at least daily.

6.2 Data Security

Only members of the CSH–RUCARES research team listed on this protocol will collect and analyze data for this study. That is, these team members will conduct sessions with all patients, even those at DDDC, and collect data using BDataPro on encrypted CSH laptops. These data will be electronic. BDataPro data and video recordings will be saved to the encrypted C:/ drives of these laptops and then transferred to a secure server at Children's Specialized Hospital or to a secure cloud server (e.g., OneDrive for Business, Box Enterprise). These data will then be deleted from the laptop's C:/ drive following the transfer in accordance with ITS procedures. The following subject identifiers will be recorded in association with the research data: Name, all elements of dates (except year) related to an individual (e.g., birth, admission, discharge, medical record numbers, and full-face photographic images). A unique subject identifying code will be used to link data to these identifiers. Subject names will be converted to initials during the subject's participation. Following completion, pseudonyms will be assigned to subjects and the pseudonym identifier will be encrypted on the server. The justification for recording these specific subject identifiers is to schedule appointments and follow up with subjects. Subject identifiers will be maintained for a minimum of six years. All electronic data (e.g., session data) will be stored on the encrypted server and any hard copy data will be stored in the client's long-term file located in a locked cabinet in a locked office. After six years, the IT department will assist with data destruction. During the course of the study, we may record sessions for data-collection purposes for children whose caregivers. These videos will be recorded through a webcam directly into an encrypted

computer and stored on the encrypted network drive or encrypted hard drive. We will delete these videos six years from the collection date or earlier (if no additional data collection is required). Research data that contain subject identifiers will not be disclosed to outside researchers who are uninvolved with the study, or to any commercial sponsor, contract research organization, or external organization or entity. Provisions in place to protect the subject's privacy include ensuring that only personnel listed on the IRB application are present during the consent process, ensuring that the fewest number of individuals possible are aware of the subject's participation in research, and ensuring that research activities are performed in as private a place as possible.

6.3 Data and Safety Monitoring

A. Data/Safety Monitoring Plan

The investigators will ensure compliance with the current Guideline for Good Clinical Practice from the International Conference on Harmonization of Technical Requirements for Registration of Pharmaceuticals for Human Use.⁴⁷ All study personnel will complete the Collaborative Institutional Training Initiative (CITI) Human Subjects Research and Good Clinical Practice courses offered online by the CITI Program. Investigators will submit annual reports to the IRB that provide information about informed consent, accrual, results, withdrawals, non-compliance, complaints and unexpected problems, as well as a risk and benefit assessment.

We will interview the primary caregiver(s) to determine how often and under what conditions the participant's destructive behavior results in physical harm to self or others. We will use this information to ensure that no participant is exposed to more risk during participation in this project than in the natural environment. We will always block or use protective equipment (e.g., arm splints) to prevent self-injurious behavior or aggression directed toward vulnerable organs (e.g., eye-gouging). Potentially harmful effects of severe head banging (e.g., detached retinas, concussions) will be mitigated by conducting sessions in a well-padded therapy room or, if necessary, having the individual wear a padded helmet. We will terminate sessions if self-injurious behavior results in reddening of the skin or frank bleeding. Further occurrences of self-injurious behavior will be blocked or prevented with protective equipment until the tissue has fully healed or the child has been examined by a nurse or physician and medically cleared to continue participation. In the Severe Behavior Program, we will routinely collect data on all adverse events (e.g., patient-to-patient aggression, staff or patient injuries), regardless of severity level. If we observe soft-tissue symptoms, they will be monitored daily and documented with images in medical progress notes until the symptoms resolve. If symptoms persist or are serious and acute, we will have a physician evaluate the child if one is immediately available, or if not, we will bring the child to a local emergency room. All adverse events will be reviewed during monthly meetings. Additionally, any unexpected or serious adverse event will be reported to the IRB, and we will respond to the adverse event as advised by the IRB. The emergence of unexpected or serious adverse events related to this study may result in removal of the participant from the study.

B. Data/Safety Monitoring Board Details

One of the postdoctoral fellows on this project will serve as the data coordinator and track the IRB application, and ensure that study personnel are using only the latest version of the protocol. In addition, this postdoctoral fellow will conduct an annual audit to ensure compliance with all IRB policies and procedures, including review of consent forms to make certain that consent forms are up to date and

are properly signed and dated. The postdoctoral fellow will report the results of the annual audit to the investigators. If corrective actions are required following the audit, the investigators and data coordinator will work with the IRB to develop correction and prevention plans. In addition, we may conduct audits on a more frequent basis if suggested by the IRB.

6.4 Reporting Results

A. Individual Subjects' Results

The results of the study for an individual participant will be shared with the parent/legal guardian of the participant at their request. The general result of all clinical procedures (i.e., not specifically those procedures conducted for the purposes of this research study) will be shared with parties for which releases of information are obtained (e.g., primary care physicians, teachers).

B. Aggregate Results

All informed consent documents will include a specific statement informing the participants that we will share the study results on ClinicalTrials.gov. We will use this website in addition to dissemination of our work through peer-reviewed publications and presentations at professional conferences.

C. Professional Reporting

We will present papers and posters by the end of the first year and throughout the entire five-year project. We will present our data at regional and national conferences hosted by organizations such as the Association for Behavior Analysis International, the Society for the Quantitative Analyses of Behavior, the Association of Professional Behavior Analysts, and the Association for Psychological Science. Beginning in the second year, we will begin publishing preliminary outcomes. We will submit papers for publication in flagship journals for behavior-analytic research, such as the Journal of the Experimental Analysis of Behavior and the Journal of Applied Behavior Analysis. In the fourth year, we will begin to summarize the findings across the larger number of accrued subjects, and we will submit these findings for publication.

D. Clinical Trials Registration, Results Reporting and Consent Posting

The research qualifies as a clinical trial that must comply with the federal requirement for public registration, results reporting and consent posting at its conclusion.

6.5 Secondary Use of the Data

N/A

7.0 Research Repositories – Specimens and/or Data

After information that could identify each participant has been removed, de-identified data collected for this research may be used by or distributed to investigators for other research without obtaining additional consent. For example, de-identified graphs of a participant's responding during the study might be re-analyzed as part of a secondary study evaluating different outcome variables.

8.0 Approvals/Authorizations

We are uploading non-Rutgers IRB approval (University of Nebraska Medical Center) and a letter of approval of an exception to allow newly recruited faculty to submit IRB applications as PIs prior to their official start dates.

## Statistical Plan

### Experiment 1

We will collect interobserver agreement on at least 33% of all sessions and ensure that the second data collector is blind to the study aims and hypotheses on one half of those observations. For Exp. 1, we will compare magnitudes of resurgence for the three treatment durations observed during the first five sessions of each resurgence test. We will report findings for each sex, in addition to reporting our aggregated data across sexes. We will apply a general linear model with two within-subject variables (individual session number and treatment duration) and one between-groups variable (treatment-duration sequence). We expect large differences between the extended-DRA condition and the short-DRA condition and a small-to-nonsignificant effect for the other paired comparisons (i.e., short vs. moderate and moderate vs. extended). Finally, model fits and comparisons for RaC and BMT will be conducted.

### Experiment 2

We will compare the prevalence and magnitude of resurgence during this RaC-informed schedule-thinning progression to that observed in the control group. We will calculate odds ratios for the likelihood of resurgence with and without RaC information on a per-case and on a per-schedule-step basis. We will apply Fisher's exact-probability statistic to test the significance of the odds ratios. With a minimum expected reduction in the per-case prevalence of 50% across 12 participants, we estimate a power of 0.89 with alpha=0.05. In addition, on a per schedule-step basis, the power increases to 0.98 with alpha=0.05. We will assess the adequacy of RaC and BMT in describing the data. Because BMT is not equipped to incorporate dynamic changes in DRA, we expect this model to poorly describe the data. RaC, however, easily incorporates such dynamic changes, and we expect the model to provide a good description of the data.

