Our preliminary data⁴⁰ suggest that DRA treatments for destructive behavior like those described below consistently produce at least 85% reduction in baseline rates of destructive behavior after 1-4 DRA sessions. Based on these results, we will set the length of our short-duration condition to approximately 4 sessions. RaC predicts that this short duration of DRA will produce high magnitudes of resurgence during a resurgence test but less resurgence than predicted by BMT. We will compare this short-duration condition with a moderate-duration condition (i.e., approximately 8 sessions of DRA) and an extended-duration condition (i.e., approximately 32 sessions of DRA). RaC predicts that, relative to the short-duration condition, the moderate-duration condition will reduce resurgence only slightly, but the extended-duration condition will reduce resurgence considerably. Each of three durations of DRA (i.e., short, moderate, and extended) will

consist of three phases, a baseline phase, a treatment phase (i.e., DRA), and an extinction phase (i.e., resurgence test). We will conduct this progression of phases three times per participant (i.e., one progression for each duration of DRA), with each progression occurring in a novel stimulus context (i.e., three contexts per participant assigned to conditions randomly), to minimize carryover effects.

Baseline- and DRA-progressive-interval assessment. We will conduct a brief, progressive-interval assessment (PIA) to identify a sufficiently dense schedule of reinforcement for use in subsequent baseline and DRA sessions. The assessment will be identical to the functional-analysis condition with the highest rates of destructive behavior (e.g., the attention condition of the functional analysis for attention-reinforced destructive behavior) with the following exceptions: (a) initially, destructive behavior will be reinforced on a dense schedule of reinforcement, (b) periods of nonreinforcement will begin and increase after every two reinforcer deliveries, and (c) the assessment will end after two reinforcement deliveries corresponding to a nonreinforcement period of 180 s or if untoward effects are observed (i.e., a burst of destructive behavior or negative emotional responding). We will use the results of the PIA to select a dense schedule of reinforcement that does not produce bursts of destructive behavior nor negative vocalizations for use in the baseline and DRA phases.

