Stimulus contexts. Reinforcement effects tend to be specific to the stimulus context in which reinforcement is delivered.⁴¹ Therefore, we will compare the effects of different durations of DRA (i.e., short, moderate, and extended) in equivalent but distinct stimulus contexts. We will correlate each stimulus context with a color, counterbalanced across participants and DRA durations. For example, we will use a blue overhead light, blue alternative communication card, and blue therapist clothing in one progression (e.g., short-DRA duration). We will correlate another progression (e.g., moderate-DRA duration) with yellow, and the final progression (e.g., extended-DRA duration) with red.

Baseline. The baselines will be identical to the functional-analysis condition associated with the highest levels of destructive behavior (e.g., the attention condition for attention-reinforced destructive behavior), except that we will reinforce problem behavior according to a dense, intermittent schedule of reinforcement, using the schedule identified from the PIA. To obtain stable rates of destructive behavior across the baseline conditions, data collection will continue for at least five sessions in each condition once the data in each condition meet the following stability criteria: (a) the standard deviation of the last five sessions is less than 50% of its mean (e.g., $M = 2$, $SD \leq 0.8$) and (b) the baseline trend is flat ($slope \leq |.05|$) or trending upward.

DRA Training. Once the above stability criteria have been met, DRA training will begin in a separate stimulus context (e.g., in a room without an overhead light, with a white alternative communication card and white therapist clothing). In most cases, exchanging a card with a picture of the child consuming the reinforcer (e.g., attention) will be used as the functional (alternative) communication response (FCR) because it can be effectively prompted using gentle physical guidance regardless of the child's functioning level (but other response options, such as card touches or vocal responses, may be used). Reinforcers for the alternative behavior are those functional reinforcers identified in the functional analysis (i.e., the consequence that maintains problem behavior in the natural environment, and the same reinforcer used in baseline). For example, the reinforcer for a child with escape-maintained problem behavior would be a break from academic, pre-academic,

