DRA. During DRA, each therapist will (a) discontinue reinforcement for destructive behavior (extinction) and (b) use a dense, intermittent schedule of reinforcement for independent (not guided) FCRs. The number of DRA sessions will depend on the current DRA-duration condition (i.e., short = approximately 4, 10-min sessions, moderate = approximately 8, 10-min sessions, or extended = approximately 32, 10-min sessions). Following each duration of DRA, participants will begin the resurgence test.

Resurgence Test. Next, we will discontinue reinforcement (i.e., program extinction) for the alternative response (i.e., the FCR), while problem behavior continues to go unreinforced. This condition will mimic lapses in the integrity with which caregivers often implement treatment in the home, school, or community settings. This phase will continue until the rate of destructive behavior is approximately 90% lower than its baseline mean for two consecutive sessions. We expect large differences in resurgence of destructive behavior between the extended-DRA condition and the short-DRA condition and a small-to-nonsignificant effect for the other paired comparisons (i.e., short vs. moderate and moderate vs. extended).

Experiment 2: Clinical study on schedule thinning.

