1.6 Study Variables

A. Independent Variables, Interventions, or Predictor Variables

Study 1.

Extended DRA. This intervention involves conducting DRA treatment for approximately 32 sessions.

Moderate DRA. This intervention involves conducting DRA treatment for approximately 8 sessions.

Short DRA. This intervention involves conducting DRA treatment for approximately 4 sessions.

Study 2.

RaC-Informed Schedule Thinning. For schedule-thinning steps, we will use the quantitative models of RaC Theory and the results of a corresponding study with nonhuman animals to dynamically adjust each upcoming schedule-thinning step. We will use additional teaching procedures (e.g., prompting, blocking) as necessary to facilitate schedule thinning, as we would clinically.

Traditional Schedule Thinning. We will look to the published literature to identify studies in which schedule-thinning was conducted arbitrarily (i.e., not in accordance with the predictions of RaC).

B. Dependent Variables or Outcome Measures

Study 1.

Rate of destructive behavior during the Resurgence Test following Extended DRA. We will collect continuous, direct-observation measures of destructive behavior throughout all phases of the study.

Rate of destructive behavior during the Resurgence Test following Moderate DRA. We will collect continuous, direct-observation measures of destructive behavior throughout all phases of the study.

Rate of destructive behavior during the Resurgence Test following Short DRA. We will collect continuous, direct-observation measures of destructive behavior throughout all phases of the study.

Study 2.

Rate of destructive behavior during RaC-informed Schedule Thinning. We will collect continuous, direct-observation measures of destructive behavior throughout all phases of the study.

Rate of destructive behavior during Traditional Schedule Thinning. We will collect continuous, direct-observation measures of destructive behavior throughout all phases of the study.

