1.9 Data Collection

A. Primary Data Collection

- **Location:** We will conduct the study within the Severe Behavior Program at CSH–RUCARES. We will conduct initial assessment and treatment in rooms with an adjacent observation window for unobtrusive measurement of behavior. We plan for almost all rooms to contain padded walls and floors to maintain patient and staff safety.

We will also conduct the study within research rooms of the DDDC. We will conduct the study within rooms with an adjacent observation window for unobtrusive measurement of behavior. All research rooms contain padded walls and floors and are approximately 3 meters by 2 meters.
- **Process of Data Collection:** Trained observers will use laptop computers with BDataPro® software developed in our lab to score frequency of participant destructive behavior and caregiver or therapist behavior. We will define destructive behavior as pushing, pinching, scratching, kicking, or biting others; hitting others with body parts or objects; banging, throwing, overturning, or tearing objects; climbing on objects not made for that purpose; striking, scratching, rubbing, poking or biting self, such that repetition has or will cause injury (e.g., eye-poking). We will convert destructive-behavior frequency to a rate by dividing the number of destructive responses in a session by the session duration in minutes. We will assess procedural integrity by scoring whether therapists correctly implemented the planned antecedents, prompts, and consequences for target responses. We will convert correct antecedents, prompts, and consequences to a percentage after dividing the number of correct responses by the number of correct-response opportunities.
- **Timing and Frequency:** We will collect data continuously during 5- or 10-min sessions during the majority of each participant's appointment (e.g., spending 2.75 hr of a 3-hr appointment in-session).
- **Procedures for Audio/Visual Recording:** We will video-record most sessions of the research for later data collection (e.g., collecting reliability or treatment-integrity data).
- **Study Instruments:** Our study does not use formal research instruments (e.g., questionnaires) but instead relies on observational data collection. See below for more information.

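### Experiment 1 leaves the scale of "magnitude of resurgence" undefined and makes no use of each progression's baseline; on the likeliest reading, a linear-scale rate, this costs anywhere from little to more than half of the power, but not validity

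*SAP*

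**What the plan says.** - **Comparison.** SAP, Experiment 1: "we will compare magnitudes of resurgence for the three treatment durations observed during the first five sessions of each resurgence test". Magnitude is not defined.
- **Model.** SAP, Experiment 1: a "general linear model with two within-subject variables (individual session number and treatment duration) and one between-groups variable (treatment-duration sequence"). No baseline term, transformation or link function is named.
- **Outcome.** Protocol 1.6 B lists one Study 1 outcome per duration, for example "Rate of destructive behavior during the Resurgence Test following Short DRA" and "Rate of destructive behavior during the Resurgence Test following Extended DRA".
- **Unit.** Protocol 1.9 A: "We will convert destructive-behavior frequency to a rate by dividing the number of destructive responses in a session by the session duration in minutes".
- **Baseline.** Under Experiment 1 in Protocol 1.3 A, each duration has its own baseline, treatment and extinction phases. In baseline, "data collection will continue for at least five sessions in each condition", under a stability rule that limits the SD of the last five sessions to less than 50% of their mean.
- **Use of that baseline.** The resurgence test runs until the rate is "approximately 90% lower than its baseline mean for two consecutive sessions". Protocol 1.3 D makes the same criterion the Study 1 primary endpoint.

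**The concern.** The protocol measures change against the baseline of the same progression, but the group test of Aim 1 does not. If the analysed quantity is the plain rate, two sources of variation stay in the duration contrast: effects that grow with a child's rate, and baseline differences between a child's three contexts. Eligibility (Protocol 4.1 C) sets a floor of more than one episode per hour and no ceiling, so rates may vary widely. Experiment 1 plans to retain 11 children (Protocol 4.3 C) and states no power. A real difference between short and extended treatment could be missed when data already collected would help to show it.

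**Working it through.** **Plan's own figure.** There is none for Experiment 1. The 0.89 in Protocol 1.5 is placed by the SAP under Experiment 2, where the test is Fisher's exact test.

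**Step 1: what the within-child comparison leaves in.** Suppose the expected rate in a test is B × p, with B the baseline rate in that context and p the fraction that resurges. Assume p = 0.70 after short and 0.35 after extended treatment.

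- B = 2/min in both contexts: 2 × 0.70 − 2 × 0.35 = 0.70/min.
- B = 3/min in both contexts: 3 × 0.70 − 3 × 0.35 = 1.05/min.
- B = 2 (short) and 3 (extended): 1.40 − 1.05 = 0.35/min.
- B = 3 (short) and 2 (extended): 2.10 − 0.70 = 1.40/min.

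The ratio p(short)/p(extended) is 2 in every line, while the raw contrast varies fourfold (1.40/0.35). Random assignment makes the last two lines equally likely. Their mean, (0.35 + 1.40)/2 = 0.875, equals 2.5 × (0.70 − 0.35). The context differences therefore add spread, not bias.

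**Step 2: simulated power, short versus extended, N = 11.** N is from Protocol 4.3 C. Everything else is assumed: two-sided alpha 0.05 (the documents state 0.05 only for Experiment 2), median baseline 2/min, 70% versus 35%, residual log-SD 0.6. Resurgence is taken as proportional to baseline raised to an exponent of 1, 0.5 or 0.

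Between-child log-SD 0.8, between-context log-SD 0.3, paired contrast:

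| Exponent | Raw rate | Proportion of baseline |
|---|---|---|
| 1 | 0.33 | 0.60 |
| 0.5 | 0.51 | 0.51 |
| 0 | 0.60 | 0.32 |

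A separate run at exponent 1, with baseline known without error, gave raw 0.31, proportion 0.59, log rate without baseline 0.59 and log ratio to baseline 0.69.

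With Poisson counts and baseline estimated from five sessions:

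- Exponent 1, between-child/between-context log-SD from 0.3/0.05 to 1.0/0.4: raw falls from 0.55 to 0.21; log ratio is 0.61 to 0.63.
- All three exponents: raw 0.21 to 0.59; log rate without baseline 0.49 to 0.66; log rate with log baseline as covariate 0.57 to 0.61.
- A further set of 12 settings: raw 0.22 to 0.59; log scale with log baseline as covariate 0.64 to 0.69.

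**Step 3: a model closer to the SAP's.** n = 12, three durations, five ten-minute sessions, six sequences, pooled error. Assumed: median baseline 3/min, short-condition resurgence 50% of baseline, extended/short ratio 0.4, exponent 1.

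| Child / context log-SD | Raw | Proportion | Log proportion | Log rate, no baseline |
|---|---|---|---|---|
| 0.3 / 0 | 0.72 | 0.72 | 0.87 | 0.89 |
| 0.6 / 0.2 | 0.57 | 0.71 | 0.87 | 0.85 |
| 0.9 / 0.4 | 0.37 | 0.70 | 0.86 | 0.76 |
| 1.2 / 0.4 | 0.29 | 0.71 | 0.84 | 0.75 |

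At exponent 0 the raw analysis has 0.74 to 0.76 and proportion of baseline 0.28 to 0.67.

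**Step 4: size of the loss.** In the counting-noise runs of step 2, the worst raw value against the lowest covariate value is 1 − 0.21/0.57 = 0.63 of the power. At small spread with exponent 1, raw 0.55 against at most 0.61 is 1 − 0.55/0.61 = 0.10.

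**Step 5: validity.** With no duration effect, the raw analysis rejected in 0.019 to 0.035 of simulated trials at nominal 0.05.

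**The case against.** **The linear rate is inferred.** The SAP says magnitude and gives no scale. The protocol's list of measures does not say what enters the model, and where the protocol judges change in Study 1 it uses the baseline mean. This stands: the firm finding is an undefined scale with no stated baseline handling. The plain rate is the best-supported reading, not an explicit statement.

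**Most of the gain is the log scale, not the baseline.** This largely stands. Each child is their own control, so a child's level cancels in a log contrast, and the contexts are meant to be equivalent. Baseline adds most when contexts differ: with context log-SD 0.4 in step 3, 0.75 to 0.76 becomes 0.84 to 0.86. It is also measured with error. An SD of 50% of the mean over five sessions gives a standard error of up to 0.50/√5 = 22%. With that much error, between-child log-SD 0.8 and context log-SD 0.2, the log ratio had 0.63 and the log rate alone 0.64.

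**Dividing by baseline can hurt.** This stands for proportion of baseline and for a fixed offset, which both force a coefficient of 1. It does not defeat a covariate, whose coefficient is estimated.

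**Stronger readings a reader might infer.** One is that a few high-rate children decide the result. The documents give no distribution of rates, and additive differences between children drop out. Another is that chance baseline differences between contexts could pass for duration effects. Contexts are assigned to conditions at random and colors counterbalanced, so these differences are error that the test already allows for, and step 5 shows no excess of false positives.

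**Conclusion.** The point holds as a gap in specification with a possible cost in power. The SAP does not define magnitude of resurgence, and its model makes no use of a baseline that the protocol collects three times per child and uses as its own yardstick. If magnitude is the rate per minute on a linear scale, power for short versus extended is about 0.2 to 0.6 under the N = 11 assumptions, against about 0.57 to 0.69 for a log-scale analysis with log baseline as covariate. The loss thus runs from little to more than half. It is largest when rates vary widely between children and resurgence scales with baseline, and it largely disappears when either condition fails. Effect size, spread and proportionality are all assumed, because the documents give none. A flat statement that power is halved would go beyond them.

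**What to change.** In the SAP, Experiment 1:

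1. Define magnitude of resurgence.
2. Analyse the first five test sessions with a log-link count model (offset log session minutes), or log rates with a stated rule for zeros, keeping session, duration and sequence and the within-child structure.
3. Add as a covariate, not a fixed offset, the log of the mean rate over the last five baseline sessions of the same progression.
4. Report proportion of baseline as a sensitivity analysis and raw rates descriptively.

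The cost is a sentence or two in the SAP, one more estimated coefficient in a small sample, and results stated as rate ratios. No new data or procedures are needed. If the sponsor already intends a baseline-relative measure, the SAP still has to say so.

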We will conduct routine-clinical and study-specific procedures with each participant approximately 3 to 6 hours per day for approximately 5 days per week for about 8-16 weeks. We expect the study-specific procedures to last approximately 3 weeks during each participant's clinical admission. Therapists will conduct approximately 15 to 30 sessions daily per participant.

D. Endpoints

The primary endpoint for Study 1 will be a rate of destructive behavior that is approximately 90% lower than the baseline mean for two consecutive sessions. The primary endpoint for Study 2 will be stable responding (standard deviation not exceeding 50% of the mean), under a terminal schedule that is similar to those found within our control group.

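### Experiment 1 analyses five sessions of every resurgence test, but a test may end after two, and the SAP does not say how unrun sessions are handled

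*SAP*

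**What the plan says.** The SAP (Statistical Plan, Experiment 1) compares the three DRA durations on resurgence "observed during the first five sessions of each resurgence test". It fits a general linear model in which session number and duration vary within child and the order of durations varies between children.

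The protocol (1.3 A, Experiment 1, Resurgence Test) sets the length of each test by the child's behavior: "This phase will continue until the rate of destructive behavior is approximately 90% lower than its baseline mean for two consecutive sessions". Section 1.3 D restates the criterion as the Study 1 primary endpoint: "a rate of destructive behavior that is approximately 90% lower than the baseline mean for two consecutive sessions". Neither place gives a minimum number of test sessions. A five-session minimum does appear in 1.3 A, "data collection will continue for at least five sessions in each condition", but under Baseline, where it governs stability before DRA begins.

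On the expected pattern, 1.3 A says that, relative to short DRA, "the extended-duration condition will reduce resurgence considerably".

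Neither document has a rule for test sessions that were not run. None of the following is mentioned: a minimum test length, carry-forward, a complete-case rule, or a model for unbalanced data.

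**The concern.** The analysis window is fixed at five sessions, while the data collection stops according to the outcome. A child whose behavior falls quickly produces a short test and leaves later cells empty. The cells are empty because the outcome was low. If the protocol's prediction is right, they would be most frequent after extended DRA, which is one side of the short-versus-extended comparison where the plan expects its largest difference.

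Two things are at stake. First, a repeated-measures general linear model in its usual form needs all 15 cells, so one short test removes the whole child. The children left would tend to be those with more, or longer, resurgence, and only 11 are expected to be retained. Second, the investigators graph and analyse the data at least daily (Protocol 6.1). If no rule is fixed beforehand, the choice between dropping children, carrying values forward and using the available sessions could be made with the results in view.

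**Working it through.** There is no figure in the plan to reproduce. Neither document states a power for Experiment 1; the SAP places the 0.89 and 0.98 under Experiment 2.

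**Inputs**
- Sessions analysed per test: 5 (SAP, Experiment 1).
- Tests per child: 3, one per duration (Protocol 1.3 A, Experiment 1).
- End of a test: two consecutive sessions about 90% below the baseline mean (Protocol 1.3 A, Resurgence Test).
- Children retained: 11 of 12 recruited (Protocol 4.3 C).
- Share q of tests that end before session 5: not given, so assumed over a range.

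**Step 1: cells per child.** Planned: 3 × 5 = 15. The rule needs two qualifying sessions in a row, so the earliest end is session 2. An end at session 2, 3 or 4 leaves 3, 2 or 1 of the five sessions unrun. The fewest cells a child can supply is 3 × 2 = 6, with 15 − 6 = 9 unrun.

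**Step 2: complete children.** If tests end early independently with the same q, all three tests reach session 5 with probability (1 − q)³. If instead the short tests always fall on the same children, the probability is 1 − q.

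| Assumed q | Independent: 11(1 − q)³ | Same children: 11(1 − q) |
|---|---|---|
| 10% | 11 × 0.729 = 8.0 | 9.9 |
| 20% | 11 × 0.512 = 5.6 | 8.8 |
| 30% | 11 × 0.343 = 3.8 | 7.7 |

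A common q is a simplification. If q differs by duration, the independent formula becomes 11(1 − q_short)(1 − q_moderate)(1 − q_extended).

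**Step 3: what produces a given q.** Suppose each session meets the 90% criterion independently with probability p (also assumed). The chance of no two consecutive qualifying sessions among the first four is (1 − p)⁴ + 4p(1 − p)³ + 3p²(1 − p)².
- p = 0.2: 0.4096 + 0.4096 + 0.0768 = 0.896, so q = 0.104.
- p = 0.3: 0.2401 + 0.4116 + 0.1323 = 0.784, so q = 0.216.
- p = 0.5: 0.0625 + 0.2500 + 0.1875 = 0.500, so q = 0.500.

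**Step 4: the handling changes the value analysed.** Take an invented test with 8% and then 6% of baseline, ended at session 2.
- Mean of available sessions: (8 + 6)/2 = 7.0%.
- Last value carried forward: (8 + 6 + 6 + 6 + 6)/5 = 6.4%.
- Unrun sessions set to zero: (8 + 6)/5 = 2.8%.
- Complete-case: the child is removed, including the other two tests.

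The plan does not select among these.

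**The case against.** The strongest reply is that nothing shows short tests will be common. The test withdraws reinforcement for the communication response, and the protocol expects temporary increases in destructive behavior at that point (1.3 A) and possibly greater risk (5.5). The team also has latitude in the word approximately and may in practice always run five sessions. Section 1.3 D defines an endpoint; it does not itself say that a test ends. And the SAP names no complete-case analysis, so dropping children is a software convention and not a stated plan.

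Most of this stands, and it limits the size of the point. In particular, two figures that a reader might use to argue that early ends are frequent do not carry that weight:
- DRA is said to "consistently produce at least 85% reduction in baseline rates of destructive behavior after 1-4 DRA sessions", which leaves at most 100 − 85 = 15% of baseline, near the 10% exit level. But that describes behavior while the alternative response is still reinforced.
- Protocol 1.1 reports resurgence in 19 of 25 applications, so none in 6 of 25 (24%). But that was during schedule thinning. A test can also show resurgence and still end before session 5, so 24% neither estimates nor bounds q.

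The reply does not remove the conflict. The stopping rule has no minimum, the analysis assumes five sessions, and nothing connects the two.

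**Conclusion.** The point holds as an unresolved conflict between the protocol's stopping rule and the SAP's analysis window, with no rule for the resulting empty cells. That much follows from the text without assumptions. It should be fixed before the Experiment 1 comparison is run.

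The size is unknown. The loss of children shown above rests on three assumptions: a complete-grid fit, an assumed q, and a stated pattern of dependence between a child's tests. If q is near zero the effect is negligible.

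A reader might infer more, but the documents do not support it:
- **Inflated false positives, or a bias that favors extended DRA.** Neither is claimed. Selection on the outcome is possible, but its direction depends on how children differ and on the effect scale, and the documents give neither. The protocol is not even uniform on the expected pattern: it predicts a considerable reduction with extended DRA and only a slight one with moderate DRA, yet expects a small or nonsignificant moderate-versus-extended difference.
- **A model that cannot be fitted.** This would need q and the number of duration sequences, and neither is stated.
- **Failure of Experiment 1 as a whole.** Only the SAP's group comparison is affected. The structured visual inspection of single-case data and the RaC and BMT model fits do not need a complete grid.

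**What to change.** Reconcile the Resurgence Test rule in Protocol 1.3 A with the five-session window in the SAP. This review does not say which should change. If five sessions are always run, stating so is enough and the model can stay.

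If a test can end before session 5, the SAP should:
1. State that no child is excluded because a test ended early.
2. Replace the complete-grid analysis with one that keeps every child, and name it as primary. There are two reasonable choices:
   - **Sessions 1-2 only.** Every test that ends under the protocol's rule supplies both, so the grid is complete and the existing model form can be used.
   - **A likelihood-based mixed model on all sessions run.** Fixed effects: duration, linear session, their interaction, and sequence. Random effects: child and child-by-duration. Use a small-sample t reference. Enter session as a trend, because a five-level factor cannot be estimated if one duration has no data at a late session. Include the baseline rate as a covariate, or analyse the proportion of baseline, because stopping depends on the rate relative to baseline. State missing at random as an assumption.
3. Use the other choice as a sensitivity analysis, and add one with the last observed rate carried forward to session 5.
4. Report the number of sessions run per condition.

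The cost is SAP wording and slightly more analysis; no new data are needed. The mixed model keeps some model dependence at about 11 children. Making sessions 1-2 primary shortens the window and gives up information on how resurgence declines.
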